1.4 Endpoints

1.4.1 Primary Endpoints

For the Randomized Cohort, the primary endpoint is

- Freedom from all-cause mortality and heart failure hospitalization at 12 months post index procedure.

For the Non-repairable Cohort, the primary endpoint is

- Freedom from all-cause mortality, and heart failure hospitalization at 12-months post index procedure.

For the Severe MAC Cohort, the primary endpoint is

- Freedom from all-cause mortality and heart failure hospitalization at 12 months post index procedure.

1.4.2 Secondary Endpoints

For the Randomized Cohort, the secondary endpoints are:

- Freedom from MR > mild (1+) in severity at 30 days post index procedure among survivors
- Freedom from all-cause mortality and mitral valve (MV) reintervention at 12 months post index procedure
- Improvement in Quality of Life (QoL), as measured by the Kansas City Cardiomyopathy Questionnaire (KCCQ) by at least 10 points at 12 months from baseline
- Proportion of Patients with New York Heart Association (NYHA) Functional Classification I or II at

Statistical Analysis Plan

12 months

- Improvement in distance walked on the 6 Minute Walk Test (6MWT distance or 6MWD) by at least 50 meters at 12 months from baseline

For the Non-Repairable Cohort, the secondary endpoints are:

- Change in QoL, as measured by the KCCQ from baseline at 6 months and 12 months
- Improvement of NYHA Functional Classification I or II at 12 months
- Change in 6MWD from baseline at 6 months and 12 months

For the Severe MAC Cohort, the secondary endpoints are:

- Freedom from MR > mild (1+) in severity at 30 days post index procedure among survivors
- Change in QoL, as measured by the KCCQ from baseline at 6 months and 12 months
- Improvement of NYHA Functional Classification I or II at 12 months
- Change in 6MWD from baseline to 6 months and 12 months

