#### 3.2 Secondary Endpoints - Randomized Cohort

The following secondary endpoints will be evaluated:

- *Effectiveness:* Freedom from MR > mild in severity at 30 days post index procedure among survivors (superiority)
- *Safety:* Freedom from all-cause mortality and MV reintervention at 12 months (non-inferiority)
- Improvement in Quality of Life (QoL), as measured by the Kansas City Cardiomyopathy Questionnaire (KCCQ) by at least 10 points at 12 months from baseline
- Proportion of New York Heart Association (NYHA) Functional Classification I or II at 12 months

- Improvement in distance walked on the 6 Minute Walk Test (6MWT distance or 6MWD) by at least 50 meters at 12 months from baseline

Additionally, if non-inferiority is demonstrated, superiority of Treatment over Control for the primary composite endpoint will also be tested.

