### **Randomized Cohort – Secondary Endpoints**

The following secondary endpoints will be evaluated. These endpoints will be evaluated for labeling claims if the primary endpoint for the randomized cohort is met.

Effectiveness: Freedom from MR > mild in severity at 30 days post index procedure among survivors

Subjects treated with the Tendyne device are expected to experience greater reduction in MR severity than subjects in the Control group. The proportion of subjects with  $MR \leq \text{mild (1+)}$  at 30 days will be compared between the Treatment and Control groups.

The null and alternative hypotheses are stated as:

$$\mathbf{H_0: P_D - P_C \leq 0}$$

$$\mathbf{H_1: P_D - P_C > 0}$$

where  $P_D$  and  $P_C$  represent the proportion of subjects with  $MR \leq 1+$  at 30 days in the Treatment and Control groups, respectively. at one-sided 2.5% significance level. The primary analysis for this secondary endpoint will be performed on the ITT population.

Safety: Freedom from all-cause mortality and MV reintervention at 12 months

The Tendyne device may reduce the risk for surgical reintervention and subjects in the Treatment group are expected to experience greater reduction in MR severity than subjects in the Control group. The proportion of subjects alive and without MV reintervention at 12 months will be compared between the Treatment and Control groups.

The null and alternative hypotheses are stated as:

$$\mathbf{H_0: \pi_D - \pi_C \leq -d}$$

$$\mathbf{H_1: \pi_D - \pi_C > -d}$$

where  $\pi_D$  and  $\pi_C$  are the true event rates for the composite of freedom from all-cause mortality and MV reintervention or reoperation at 12 months in the Treatment and Control group, respectively, and  $d$  is the non-inferiority margin of 10%. [REDACTED]

[REDACTED]  
a one-sided test with 2.5% significance level. [REDACTED]

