##### Freedom from MR > mild in severity at 30 days post index procedure

To evaluate whether the Tendyne system is more effective at reducing MR than a pre-specified performance goal [REDACTED], freedom from MR > mild (1+) at 30 days post index procedure will be tested against a PG.

The null and alternative hypotheses are stated as:

$$H_0: P_{MR \leq 1+} \leq P_{PG}$$

$$H_1: P_{MR \leq 1+} > P_{PG}$$

where  $P_{MR \leq 1+}$  is the proportion of subjects who have  $MR \leq 1+$  at 30 days post index procedure.  $P_{PG}$  is set at 75%.

The null hypothesis will be rejected at the one-sided 2.5% significance level [REDACTED].

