1.5 Randomization

1.5.1 Randomized Cohort

Approximately 382 subjects will be randomized 1:1 in the primary analysis (treatment vs. control).

An Electronic Data Capture (EDC) system will be used to randomize subjects.

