2.3.1.2 Randomized Cohort – Secondary Endpoints

The following secondary endpoints will be evaluated. These endpoints will be evaluated for labeling claims if the primary endpoint for the Randomized cohort is met. The primary analysis population for all secondary endpoints of the Randomized cohort is ITT.

2.3.1.2.1 Freedom from MR > mild (1+) at 30 days post index procedure among survivors

Subjects treated with the Tendyne device are expected to experience greater reduction in MR severity than subjects in the Control group. The proportion of subjects with $MR \leq \text{mild (1+)}$ at 30 days will be compared between the Treatment and Control groups.

The null and alternative hypotheses are stated as:

$$H_0: P_D - P_C \leq 0$$

$$H_1: P_D - P_C > 0$$

where P_D and P_C represent the proportion of subjects with MR \leq mild (1+) at 30 days post index procedure in the Treatment and Control groups, respectively. [REDACTED]

at one-sided 2.5% significance level.

In the case that the 1-month follow-up visit is missed, or the subject's MR measurement is not available from this visit for some reason, the chronologically nearest post-procedure MR measurement obtained from the core lab, within 365 days of the scheduled 1-month follow-up visit, will be used instead.

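### The 30-day MR endpoint is limited to survivors in the endpoint lists but assigned to ITT or AP populations for testing, with no visible rule for deaths before 30 days

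*SAP*

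**What the plan says.** **Randomized cohort.** SAP 1.4.2 lists freedom from MR > mild (1+) "in severity at 30 days post index procedure among survivors". Protocol 3.2 has the same condition and labels the test superiority, and the headings above the hypotheses (Protocol 10.2.1, SAP 2.3.1.2.1) repeat it. On the population, SAP 2.3.1.2 states: "The primary analysis population for all secondary endpoints of the Randomized cohort is ITT". Protocol 10.2.1 agrees: "The primary analysis for this secondary endpoint will be performed on the ITT population". The hypotheses define P_D and P_C as proportions of subjects, without a survivor condition. The test is run "at one-sided 2.5% significance level" and can support a label: "These endpoints will be evaluated for labeling claims if the primary endpoint for the Randomized cohort is met".

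**Severe MAC cohort.** The endpoint lists (Protocol 3.4, SAP 1.4.2) restrict the endpoint to survivors. The hypothesis text does not: Protocol 10.2.3 says freedom from MR > mild "at 30 days post index procedure will be tested against a PG". SAP 2.3.3.2.1 and the testing order in SAP 2.11.3 also omit the restriction, and SAP 2.3.3.2 names the AP population. The goal is 75%, and this endpoint comes first in the sequence.

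**Missing readings.** For the Randomized cohort, SAP 2.3.1.2.1 replaces an unavailable 1-month MR value with the nearest post-procedure core-lab reading within 365 days of the scheduled visit. It does not say whether this covers subjects who died. Protocol 7.4.6 requires a pre-discharge TTE, so many such subjects would have a reading.

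**The concern.** Survivors only, and everyone randomized or attempted, are different denominators for the same hypothesis test. A subject who dies on day 20 could be dropped as a non-survivor, counted as a failure in the full population, or counted as a success on the discharge echo. The visible text does not choose among these, so two analysts could report different results from the same data.

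In the Randomized cohort the choice also affects what the comparison means. Being alive at 30 days follows randomization and may differ between arms; the protocol's rationale (2.1.8) itself calls the transapical procedure more invasive. A survivors-only difference does not describe everyone randomized, and the result may be quoted in labeling. In Severe MAC there is no randomized comparison to protect, but a fixed goal makes the pass mark depend on the denominator.

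**Working it through.** The planning rates and power for this endpoint are redacted (SAP 2.4.1.2.1), so there is no stated figure to reproduce. The check uses proxies and assumed ranges.

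**Inputs**
- n = 382/2 = 191 per arm (SAP 1.3).
- p_D = 0.988: trace MR or less at one month in the earlier Tendyne study (Protocol 2.1.7). This is stricter than <= mild, so conservative.
- p_C = 0.69 or 0.62: one minus the 31% and 38% with MR > 1+ after MitraClip (Protocol 2.1.8). These are 12-month figures, assumed here for 30 days.
- q_D, q_C = 30-day mortality by arm. The documents give none for the randomized population, so both are assumed. The only anchors are no operative deaths in the first 100 Tendyne subjects and 1/20 (5%) in severe MAC (Protocol 2.1.7).

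**Formulas**
- Survivors only: p_D − p_C
- All randomized, death as failure: p_D(1 − q_D) − p_C(1 − q_C)
- Shift: p_D·q_D − p_C·q_C

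**Worked case**, p_C = 0.69, mortality 5% vs 1%: survivors only 0.988 − 0.69 = 29.8 points. All randomized: 0.988 × 0.95 − 0.69 × 0.99 = 0.9386 − 0.6831 = 0.2555, about 25.6 points. Shift: 0.0494 − 0.0069 = 0.0425, about 4.3 points.

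| q_D vs q_C | All-randomized difference (p_C = 0.69) | Survivors-only minus all-randomized |
|---|---|---|
| 1% vs 1% | 29.5 | +0.3 |
| 2% vs 1% | 28.5 | +1.3 |
| 5% vs 1% | 25.6 | +4.3 |
| 10% vs 1% | 20.6 | +9.2 |
| 1% vs 2% | 30.2 | −0.4 |
| 2% vs 5% | 31.3 | −1.5 |

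With p_C = 0.62, 36.8 points becomes 32.5 at 5% vs 1% and 27.5 at 10% vs 1%.

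**Direction.** Survivors-only is larger only when q_D/q_C > p_C/p_D, that is 0.69/0.988 = 0.70 or 0.62/0.988 = 0.63.

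**Effect on the conclusion.** With deaths as failures, 191 per arm and one-sided 2.5%, power stays at or above 99.8% for q_D up to 10%. With q_C = 1% it falls to 90% only at q_D of about 16.5% (p_C = 0.69) or 22.5% (p_C = 0.62).

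**Error rate.** If the true all-randomized difference were zero, the survivors-only test would reject 7.5% to 8.9% of the time at 5% vs 1% mortality, 2.5% at equal mortality, and 0.8% to 1.0% at 2% vs 5%. This null is far from the expected effect, but the nominal 2.5% then applies to survivors, not to all randomized.

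**Severe MAC.** Assume n = 103, goal 75%, an exact one-sided 2.5% binomial test (the method is redacted), 5 deaths before 30 days (103 × 5% ≈ 5), and an MR reading in every survivor.
- Survivors only, n = 98: 83 successes needed (84.7%, p = 0.0145; 82 gives p = 0.027).
- All AP, deaths as failures, n = 103: 87 needed (84.5%, p = 0.0144; 86 gives p = 0.026).

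So 83 to 86 successes pass on one denominator and fail on the other.

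**The case against.** A reader might infer that the survivor restriction overstates the Tendyne effect as a matter of fact. The documents do not support that. They give no 30-day mortality by arm for the randomized population, the 5% figure comes from 20 severe MAC patients, and the sign reverses when Tendyne mortality is clearly lower. Deaths are left out rather than scored as successes, so the gap is between two estimands.

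A reader might also infer that early deaths disappear from the evaluation. They do not. Death counts in the gating primary endpoint and in the next secondary endpoint, 30-day mortality is reported, and MVARC Device Success at 30 days combines procedural death with MR reduction. This stands, although the gate is a non-inferiority test with a 12.5-point margin at one-sided 5%. It does not exclude an early mortality excess or alter the MR difference that would be quoted.

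Finally, ITT may mean analysis by assigned arm within a declared survivor restriction. The restriction is stated openly for the Randomized cohort, and the ITT definition, missing-data detail and tipping-point appendix are redacted, so an outright contradiction there is not established, nor is the removal of every early death. This argument does not cover Severe MAC, where the visible hypothesis and testing-order text omits the restriction that the endpoint lists impose.

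**Conclusion.** The point holds as a matter of definition: a tested, label-eligible endpoint has no single stated denominator, and the visible text has no rule for early deaths. In the Randomized cohort the shift is about 4.3 points on a difference of roughly 30 to 37 points at an assumed 5% vs 1% mortality. It is near zero at equal low mortality and reverses if Tendyne mortality is clearly lower. The superiority conclusion is unlikely to change. These sizes rest on a single-arm Tendyne rate, 12-month control rates and assumed mortality.

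In Severe MAC the choice could decide the first gated secondary test, but only in a narrow window: 83 to 86 successes among 98 survivors (84.7% to 87.8%) under the stated assumptions, well below the MR results reported in earlier Tendyne experience. The matter is minor but cheap to settle before analysis.

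**What to change.** 1. State one denominator for the 30-day MR endpoint and use it in the endpoint lists, hypothesis sections and testing order of both documents.
2. State in SAP 2.3.1.2.1 that the 365-day fallback does not apply to subjects who died before 30 days.
3. Prespecify an analysis of alive with MR <= mild (1+) at 30 days on all ITT or AP subjects, with deaths as failures, reported beside the survivors-only result. Make it the tested version or, at least, a required sensitivity analysis.
4. For Severe MAC, match the tested denominator to the one from which the 75% goal was derived. That justification is redacted in SAP Appendix I, part E, so the sponsor must confirm it.

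Cost: wording changes and one small extra analysis, with no new data. The MR proportion reported with deaths as failures would be slightly less favourable.

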1.4.3 Descriptive Endpoints

Additional descriptive endpoints include:

1.4.3.1 Clinical Endpoints:

- All-cause mortality, CV hospitalizations, all stroke or MV reintervention or reoperation, at 2 years post index procedure and then yearly through 5 years
- Change from baseline in distance walked on the 6MWT at each follow-up visit
- Change from baseline in QoL, as measured by the KCCQ at each follow-up visit
- Change from baseline in health outcomes, as measured by the EQ-5D questionnaire, at each follow-up visit
- Change from baseline in health outcomes, as measured by the 12-item Short Form Health Survey (SF-12), at each follow-up visit
- NYHA Functional Classification at each follow-up visit
- Number of days alive and out of hospital from the time of the index procedure to 12 months, and then yearly through 5 years
- Length of index hospitalization for procedure
- Annualized rate of heart failure hospitalizations
- Change from baseline in BNP or NT pro-BNP levels, at all follow-up visits
- All-cause mortality at 30 days, 1 year and then yearly through 5 years

Statistical Analysis Plan

1.4.3.2 MVARC Endpoints:

The following Mitral Valve Academic Research Consortium (MVARC) measures of success will be captured for the Randomized, Non-repairable and Severe MAC Cohorts.

- Technical Success
- Device Success
- Procedural Success
- Patient Success

The definitions for the above endpoints can be found in Appendix II of Protocol CS0004-P, the SUMMIT clinical trial.

1.4.3.3 Echocardiographic Endpoints:

The following echocardiographic endpoints, as adjudicated by the Echocardiography Core Laboratory, will be reported at baseline, discharge, 1 month, 6 months, 12 months, and then annually through 5 years. For continuous variables, change from baseline to each follow-up will also be reported:

- MR severity grade
- Effective Regurgitant Orifice Area (EROA)
- Regurgitant Volume
- Regurgitant Fraction
- Left Ventricle End Diastolic Volume (LVEDV)
- Left Ventricular End Systolic Volume (LVESV)
- Left Ventricular End Diastolic Dimension (LVEDD)
- Left Ventricular End Systolic Dimension (LVESD)
- Left Ventricular Ejection Fraction (LVEF)
- Right Ventricular Systolic Pressure (RVSP)
- Mitral Valve Area
- Mean Mitral Valve Gradient
- Mean Left Ventricular Outflow Tract Gradient
- Cardiac Output
- Forward Stroke Volume

Statistical Analysis Plan

1.5 Randomization

1.5.1 Randomized Cohort

Approximately 382 subjects will be randomized 1:1 in the primary analysis (treatment vs. control).

An Electronic Data Capture (EDC) system will be used to randomize subjects.

1.5.2 Timing of Randomization

Subjects will be randomized after the investigational site personnel have confirmed and documented that the subject has met all eligibility criteria, the imaging core labs have confirmed anatomic suitability, and the SEC has concurred with the local site heart team that the subject has been treated per applicable standards and can be treated in the Randomized cohort of the trial.

1.6 Blinding

2.0 ANALYSIS CONSIDERATIONS

2.1 Analysis Populations

2.1.1 Randomized Cohort

The Intention-to-Treat, modified Intention-to-Treat and Per-Protocol are defined below. For analyses of the Randomized Cohort, the duration of follow-up will be calculated from the date of registration.

2.1.1.1 Intent-to-Treat (ITT) Population

2.1.1.2 Modified Intention-to-Treat (mITT) Population

2.1.1.3 Per-Protocol (PP) Population

Statistical Analysis Plan

2.1.2 Non-repairable and Severe MAC Cohorts

2.1.2.1 Attempted Procedure (AP) Population

[REDACTED]

2.2 Statistical Methods

2.2.1 Descriptive Statistics for Continuous Variables

For continuous variables (e.g., age, LVEF, LVEDV), results will be summarized with the numbers of observations, means, standard deviations, quartiles, minimums, maximums, and 95% confidence intervals. Differences between the treatment groups, if applicable, will be summarized with differences of the two means, and 95% confidence intervals for the difference between the means.

2.2.2 Descriptive Statistics for Categorical Variables

For categorical variables, such as sex and NYHA classification, results will be summarized with subject counts and percentages/rates, and with exact 95% [REDACTED] confidence intervals. Differences between the two treatment groups, if applicable, will be summarized with the difference in proportions and [REDACTED] 95% confidence interval for the difference of two proportions.

2.2.3 Survival Analyses

Survival analysis will be conducted to analyze time-to-event variables. Subjects without events will be censored at their last known event-free time point when they stay in the study. Survival curves will be constructed using Kaplan-Meier estimates.

2.3 Endpoint Analysis

As the Coronavirus Disease 2019 (COVID-19) pandemic has spread around the globe, the following analysis mechanism will be implemented to minimize the potential confounding effect from this emerging infectious disease for the trial primary and secondary endpoints set forth in assessing trial success and labeling claims. In alignment with the guidance document “FDA Guidance on Conduct of Clinical Trials of Medical Products during the COVID-19 Public Health Emergency” updated 03-June-2020, and EU “Guidance on the Management of Clinical Trials during the COVID-19 (Coronavirus) Pandemic” updated 28-April-2020, additional consideration was given to the impact of the COVID-19 pandemic on the primary and secondary endpoints analyses for this study. As such, prespecified methods are included in

Statistical Analysis Plan

the sections that follow to indicate the handling of any outcomes impacted by COVID-19 as well as efforts to minimize missing endpoint data during the COVID-19 pandemic.

Any subject experiencing a CEC-adjudicated COVID-19-related hospitalization or death, indicated as 'related' within the associated event adjudication by the CEC, will have any and all follow-up clinical data censored beginning with the event. That is, the follow-up data will not contribute toward any primary or secondary endpoint analysis for any of the 3 cohorts, with the exception of MR severity, which will be used for all subjects in all cohorts in whom MR data are available. Furthermore, any subject having a COVID-19 infection but not experiencing a CEC adjudicated COVID-19-related hospitalization or death, as defined above, will not be censored and their data, barring other protocol deviations, will contribute in its entirety to the analysis of all endpoints.

2.3.1 Randomized Cohort

2.3.1.1 Randomized Cohort – Primary Endpoint

The primary endpoint for the randomized cohort is freedom from all-cause mortality and heart failure hospitalization (HFH) at 12-months post index procedure. The trial is intended to demonstrate non-inferiority of the Tendyne™ Transcatheter Mitral Valve System to TEER with MitraClip for the treatment of moderate-to-severe or severe MR.

The null (H_0) and alternative (H_1) hypotheses¹⁰ are:

$$H_0: \pi_D - \pi_C \leq -d$$

$$H_1: \pi_D - \pi_C > -d$$

where π_D and π_C are the true event rates for the composite of freedom from all-cause mortality and HFH at 12 months in the Treatment and Control group, respectively, and d is the non-inferiority margin. The non-inferiority margin is set at 12.5%.

The primary analysis for the primary endpoint will be performed on the ITT population. The analysis will also be performed on the mITT and PP populations.

using a one-sided test with a 5% significance level.

If the primary endpoint passes the non-inferiority test, it will then be tested, following secondary endpoints, for superiority of Tendyne vs. MitraClip at two-sided 5% significance level.

The justification of the non-inferiority margin d of 12.5% will be provided in the Appendix. Additional analysis populations and sensitivity analyses to address missing data are described in **Sections 2.8 and 2.13**.

Statistical Analysis Plan

2.3.1.2 Randomized Cohort – Secondary Endpoints

The following secondary endpoints will be evaluated. These endpoints will be evaluated for labeling claims if the primary endpoint for the Randomized cohort is met. The primary analysis population for all secondary endpoints of the Randomized cohort is ITT.

2.3.1.2.1 Freedom from MR > mild (1+) at 30 days post index procedure among survivors

Subjects treated with the Tendyne device are expected to experience greater reduction in MR severity than subjects in the Control group. The proportion of subjects with $MR \leq \text{mild (1+)}$ at 30 days will be compared between the Treatment and Control groups.

The null and alternative hypotheses are stated as:

$$H_0: P_D - P_C \leq 0$$

$$H_1: P_D - P_C > 0$$

where P_D and P_C represent the proportion of subjects with MR \leq mild (1+) at 30 days post index procedure in the Treatment and Control groups, respectively. [REDACTED]

at one-sided 2.5% significance level.

In the case that the 1-month follow-up visit is missed, or the subject's MR measurement is not available from this visit for some reason, the chronologically nearest post-procedure MR measurement obtained from the core lab, within 365 days of the scheduled 1-month follow-up visit, will be used instead.

